2.2 Summary of Benefits and Risks

The expected benefits of the surgery outweigh the expected risks. The benefit of the surgery is expected to be improved knee functionality. The risk in the operated group are the normal risks of every surgery, like pain and redness of the interventional side, side effects of anaesthesia. The patients not operated do not have the risks applying to any surgery. For this patient group, there is an extremely limited possibility that the knee functionality will improve. Another benefit for both groups is the close follow-up of the knee functionality. The non-operated patients can, at any time point, decide to be operated.

Benefit Summary

Since only patients with partial meniscal loss are included, only through allogeneic partial meniscal implantation with Spongioflex® the lost function of the corresponding meniscus can be improved, and the graft will convert into endogenous tissue without recalcification[5]. For the patient group, which will not be operated there is a limited possibility that the meniscal function will improve. The psychological benefit for the operated group will be that they can better perform for their daily life duties.

The collagenous meniscus implant (CMI) has been withdrawn from the market. There is currently no alternative made of biological material. Spongioflex® does not affect the body's metabolism and does not influence the effect of medications the patient is taking. There are no restrictions for the patient for any medication. Allogeneic meniscal partial implantation is a standard orthopedic surgical technique that can be performed minimally invasively with arthroscopic support. Systemic side effects (e.g., transmission of infectious diseases) are not known after intra-articular application of freeze-preserved tissue grafts from the non-profit German Institute for Cell and Tissue Replacement (DIZG gGmbH). The grafts are sterilized using a validated sterilization procedure, and extensive donor screening is performed in accordance with regulatory requirements.

A case report[31] shows that the procedure was performed with no complications.

The benefit to society is that gonarthrosis will be postponed as well as TKA and thus the patient is able to work under better conditions, and longer before invalidity.

The hospital, where the procedure was performed, is available 24h/7days a week when problems occur.

Risk Summary and Mitigation Strategy

Trial-specific Discussion of Intervention Risks and Mitigations

There is a risk that even though the partial meniscal replacement is performed, the knee functionality will not improve. Strict inclusion and exclusion criteria should limit the number of cases without a benefit (see inclusion and exclusion criteria). The treatment would be the same, participating or not on the trial. Study specific is to fill the questionnaires at the planned visits (IKDC and KOOS, CRF).

Trial-specific Discussion of Procedure Risks and Mitigations

The procedure risks are the risk of any surgery for the operated group. The non-operated group does not have any surgical risk. They have the risk that the knee functionality will deteriorate. Due to the close follow-up, also for these patients, they can minimize this risk by deciding to change into the operated group.

Trial-specific Discussion of Other Risks and Mitigations

There are no other risks. There are no comparators, challenge agents or medical devices.

Overall Benefit: Risk Conclusion

The overall risk is very low, because partial meniscal replacement is an established operative procedure.

There are the normal risks applying to any surgical procedure. For the non-operated group, there are no surgical risks.

The benefit for the surgical group is the possibility of improvement of knee functionality. The benefit for the non-operated group is the close follow up to monitor the properties of the meniscus. This will help to decide to switch to the surgery group. The risks are assessed at least once a year for up to 2 years. After this treatment related risks are not expected. The 5-year visit is scheduled to verify the properties of the meniscus and to evaluate the exploratory outcome of progression of osteoarthritis up to TKA.

3 TRIAL OBJECTIVES, ENDPOINTS AND ESTIMANDS

3.1 Primary Objective + Associated Endpoint and Estimand

| Primary Objective | Primary Endpoint |
|---------------------------------------|--|
| To evaluate efficacy of the procedure | Improvement of PROMs (KOOS, IKDC, VAS Pain Score) 2 and 5 years after surgery compared to scores of the non-operated group and compared to pre-surgery scores. |

Primary Estimand (Variable): Difference in PROMs after 2 and 5 years

Endpoint: 2 and 5 years after surgery/enrollment, or progression to TKA

Treatment: varies with the group chosen by the patient (operated or not operated)

Population: male and female patients between 18 and 60 years

Intercurrent event: progression of osteoarthritis up to TKA, lost to follow up, premature death, the patient wishes to change to the operated group after a certain time (The process: progression of osteoarthritis is very slow. It will be very unlikely that more than 1 patient wants to change to the operated group within the 5 years of the trial. The same is true for progression to TKA. The possibility to change later in the operated group will take off the pressure from the patient to make the “wrong” decision now.)

Population-level summary: The primary objective is to compare the PROM change from baseline between the operated and non-operated group after 2 and 5 years. The difference in obtained PROMS will be evaluated.

Estimand Description: The Estimand are the Difference in PROMs. This includes specific knee scores (IKDC, KOOS) and the VAS-Pain Score. IKDC and KOOS have values between 0 and 100 and the higher they are as better the function of the knee. The VAS Pain Score has values between 0 and 10 and the higher the score the higher the pain.

3.2 Secondary Objective + Associated Endpoint and Estimand

| Secondary Objective | Secondary Endpoint |
|---------------------------|---|
| Safety of the patient | Type, frequency and severity of treatment-related AEs and SAEs . |
| Efficacy of the procedure | How many patients show a progression of osteoarthritis up to TKA? |
| MRI evaluation | Outerbridge graduation, size of meniscus, number of patients with extrusion, size of extrusion after 6 weeks, 6 and 12 months (for operated patients) and after 2 and 5 years, comparison between the operated and the non-operated group |
| Patient satisfaction | very pleased, pleased, not pleased, very unsatisfied in the operated group after 2 and 5 years. |

Secondary Estimand(Variable): Safety of Patient: Number of AE and SAE, Efficacy of the procedure:

Number of patients with progression of osteoarthritis up to TKA, MRI evaluation: Change in Outerbridge graduation from baseline and patient satisfaction.

Endpoint: 2 and 5 years after surgery/enrollment, or progression to TKA

Treatment: varies with the group chosen by the patient (operated or not operated)

Population: male and female patients between 18 and 60 years

Intercurrent event: progression of osteoarthritis up to TKA; lost to follow up, premature death, the patient wishes to change to the operated group after a certain time (The process: progression of osteoarthritis is very slow. It will be very unlikely that more than 1 patient wants to change to the operated group within the 5 years of the trial. The same is true for progression to TKA. The possibility to change later in the operated group will take off the pressure from the patient to make the “wrong” decision now.)

Population-level summary: The secondary objective is safety of the patient, efficacy of the procedure, MRI evaluation and patient satisfaction. Type, frequency and severity of treatment-related AEs and SAEs will be evaluated and how many patients show a progression of osteoarthritis up to TKA, to compare the MRI image from baseline and patient satisfaction after 2 and 5 years.

Estimand Description

Safety of the patient and efficacy of the procedure: if AE, SAE or SUSARs are reported, the benefit-risk balance evaluation will be renewed, and it will be decided if the study will be continued.

MRI Image will be evaluated using the Outerbridge [1] graduation, the size of the meniscal defect and the meniscus itself, the MRI signal of the meniscus will be evaluated after a modified score after Genovese et al.[32] and if there is an extrusion and which size the extrusion has. Patient satisfaction will be categorized as: very pleased, pleased, not pleased, very unsatisfied and will be evaluated using the Chi-square test.

3.3 Exploratory Objective + Associated Endpoint and Estimand

| Exploratory Objective | Exploratory Endpoint |
|--|---|
| How many patients show a progression of osteoarthritis up to TKA | Progression of osteoarthritis up to TKA |

Exploratory Estimand (Variable): Progression of osteoarthritis up to TKA

Endpoint: 2 and 5 years after surgery/enrollment

Treatment: varies with the group chosen by the patient (operated or not operated)

Population: male and female patients between 18 and 60 years

Intercurrent event: lost to follow-up, premature death

Population-level summary: the explorative objective is: how many patients have a progression of osteoarthritis up to TKA, in the operated and non-operated group.

Estimand Description:

The number of patients with progressing of osteoarthritis up to TKA will be evaluated using the Kaplan Meier estimator for time to event.

4 TRIAL DESIGN

4.1 Description of Trial Design

Description of Intervention Model

This investigator initiated; low intervention trial is performed with 2 groups. The intervention group is the group of patients who will be operated. The control group are the patients not willing to be operated. Due to the incidence of patients with partial meniscal loss in the last years in the private praxis of the principal investigator 30 patients in the operated group and 10 patients in the non-operated group will be recruited within 2 years of recruitment. The study will be performed to prove patient safety and efficacy of the procedure. The process of progression of osteoarthritis is very slow. It will be very unlikely that more than 1 patient will be in this situation and wants to change to the operated group within the 5 years of the trial. The same is true for progression to TKA. The possibility to change later in the operated group will take off the pressure from the patient to make the “wrong” decision now.

Description of Trial Duration

The total trial duration will be 7 years. The recruitment period will be 2 years. Follow-up is 5 years. Depending on, if the patient will be operated or not, the time until surgery will add on these 5 years. The substance used (human cancellous bone) does not have a dose. It will be used in various dimensions.

Method of Assignment to Trial Intervention

This is a single centre trial. The initiator of the trial will perform the trial on its own. Due to the small number of patients included, the investigator will perform all visits on its own. There is no randomization. The patient decides if he/she will be operated or not. There is no blinding. A clinical monitor will perform data monitoring. There are no plans for a data monitoring committee due to the small number of patients and small number of data recorded. Bias is minimized by investigating the MRI images after a standardized protocol. The PROMs are filled in by the patient without the help of the investigator. The analysis will be performed by the investigator using statistical software. Patients from the non-operated group can transition to the operated group at any time. There are no rules for transition.

An interim analysis is planned after 2 years. See details in section 9.7

There will be no sample collection during the trial. In the moment there is no extension of the trial over the 5 years planned.

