4.3 Access to Trial Intervention After End of Trial

If the trial shows benefit for the patient the procedure will be performed after the trial as standard procedure by the investigator.

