9 STATISTICAL CONSIDERATIONS

Data analysis complies with ICH E9 Guideline and ICH E9(R1) Guideline. This clinical trial is to confirm patient safety and efficiency of the procedure.

For this reason, as primary objective PROMs (IKDC, KOOS and VAS-pain score) will be evaluated before surgery/at the beginning of the trial and then starting at 6 months after surgery/beginning of the trial for the operated or non-operated group, respectively. The evaluation will be performed also after 12 and 24 months and after 5 years. A primary analysis will be performed 2 years after surgery/start of the trial.

At the beginning of the trial and prior to operation demographic and baseline data will be collected and summarized for both groups.

For safety, there will be an evaluation of complications, AE, SAE and SUSARs at each follow-up visit (at the end of the hospital stay, after 6 weeks, after 6, 12, 24, months and after 5 years, for the operated group). The number of AE, SAE and SUSARs will be recorded and evaluated at each visit. MRI evaluation starts at the follow-up visit 6 weeks after surgery for the operated group and 24 months after the start of the trial for the non-operated group. The evaluation of the MRI will be performed after a modified graduation of Genovese et al. [32]. Additionally, there will be the meniscal size evaluated and if there is an extrusion of the meniscus and how big the extrusion is. There will be a Kaplan-Meier-time to event curve for both groups regarding progression of osteoarthritis up to TKA. The analysis will be conducted on all participant data after 2 years and after 5 years.

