9.5 Safety Analyses

Patient safety will be analyzed by recording AE, SAE and SUSARs. The number of these events will be recorded and compared for both groups. SUSARs will only occur, if any, in the operated group. The frequencies obtained will be displayed in bar plots and tables with group comparisons based on Fisher's exact test. Safety is a secondary outcome and is described in detail in 9.3.

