9.7 Interim Analyses

Interim analysis will be performed 2 years after surgery/start of the trial. After knee surgery, the usual follow up is 2 years. Because long term results are important for the efficacy of the procedure, evaluations will be performed also after 5 years. The analysis will be performed by the investigator. The statistical methods used are described under 9.2 and 9.3. The outcome data will be seen only by the investigator while the trial is ongoing. The 2-years result will be published in an international orthopedic journal. There will be no group sequential test and no spending function. The number of patients is fixed at 30 in the operated group and at 10 in the non-operated group. There will be no enrollment until an event occurs. There will be no trial adaptation or changes to the eligibility criteria.

Stopping criteria are: If AE, SAE and SUSARs change the benefit-risk balance, there will be a new benefit-risk balance evaluation and after this evaluation it will be decided if the trial will be stopped. The investigator expects a maximal 20% failure rate of the procedure. If the failure rate is higher a new benefit-risk balance evaluation must be performed and after the evaluation it must be decided if the trial continues. If the safety of the patients is not any more given, the trial should be stopped.

The investigator also has the right to stop the trial. This could be because of the closure of the site. See 10.5 for details.

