9.8 Sample Size Determination

The unpaired t-Test will be used for normally distributed PROMs. Values for the primary outcome are expected to be about 55/84 for the IKDC score and 46/86 for the KOOS pre/postsurgery, respectively. For this calculation, the program G-power was used. A sample size of 9 in the operated group and 3 in the non-operated group would be sufficient to reach a power of 0.982. When we include 10 non-operated patients and 30 operated patients the effect size is 2.0, $\alpha = 0.00655$ and the power is than 0.993. If we have a 20% lost to follow-up, the numbers of patients will be 8/24 and $\alpha = 0.014$ and the power will be 0.985. The number of 30/10 is sufficient to reach a power of >0.8.

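### The protocol says the trial will prove or confirm patient safety, but 30 implants tested against 10 controls can only describe it: zero SAEs in 30 still leaves a two-sided 95% upper limit of 11.6%

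*Protocol*

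**What the plan says.** Two places in the protocol state what the trial will establish about safety. Section 4.1: "The study will be performed to prove patient safety and efficacy of the procedure". Section 9, in its opening paragraph: "This clinical trial is to confirm patient safety and efficiency of the procedure".

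The operative text is more modest. Section 3.2 lists safety as a secondary objective, measured by the type, frequency and severity of treatment-related AEs and SAEs, and 9.5 again calls it secondary. On analysis, 9.5 says: "The frequencies obtained will be displayed in bar plots and tables with group comparisons", using Fisher's exact test. Section 9.1 also names Fisher's test, while 9.3 names a Chi-square test for the same comparison. Section 9.3 adds that SUSARs can arise only in the operated group and so have nothing to be compared with.

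On size, 9.7 says: "The number of patients is fixed at 30 in the operated group and at 10 in the non-operated group". Section 4.1 derives these numbers from the practice's caseload: "Due to the incidence of patients with partial meniscal loss in the last years in the private praxis of the principal investigator 30 patients". The only sample-size argument, in 9.8, concerns the patient-reported scores: "The unpaired t-Test will be used for normally distributed PROMs". The only hypothesis, in 9.2.1, also concerns those scores.

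**The concern.** Proving or confirming safety implies that the trial can exclude an unacceptable event risk. To do that, a plan needs a risk to exclude, or a margin against control, and enough patients to exclude it. The protocol has neither. The 20% limit in 7.4, 8.2, 9.3 and 12.1 concerns failed procedures, not SAEs.

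The analysis that is fixed is a test of difference. At 30 against 10, such a test will usually be non-significant whether or not the implant carries a material risk. Paired with an aim worded as proof, a null p-value or a zero SAE count is open to being reported as the promised confirmation. That matters here because the only clinical experience the protocol cites for this procedure is a case report (2.2, 6.2), and 9.7 commits to publishing the 2-year result.

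**Working it through.** **Inputs.** 30 operated and 10 non-operated patients (9.7); Fisher's exact test (9.1, 9.5) or Chi-square (9.3); significance at p < 0.05 (9.2). The protocol gives no expected or acceptable event rate, so every true rate below is an assumption. Each patient is counted once, as having or not having an event.

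**1. The plan's own figure.** Section 9.8 states: "When we include 10 non-operated patients and 30 operated patients the effect size is 2.0, $\alpha = 0.00655$ and the power is than 0.993". For a two-sided unpaired t-test the noncentrality is 2.0 × √(30 × 10 / 40) = 5.48 on 38 degrees of freedom, and the power is 0.9935. For 24/8 with α = 0.014 the noncentrality is 2.0 × √(24 × 8 / 32) = 4.90 on 30 degrees of freedom, and the power is 0.9857 (stated 0.985). Both figures reproduce. They concern the scores and say nothing about safety.

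**2. What zero SAEs in 30 implants would show.** With 0 events in n, the exact (Clopper-Pearson) upper limit is 1 − 0.025^(1/n) two-sided and 1 − 0.05^(1/n) one-sided.
- Two-sided 95%: 1 − 0.025^(1/30) = 0.1157, or 11.6%.
- One-sided 95%: 1 − 0.05^(1/30) = 0.0950, or 9.5%.
- If the true SAE risk were 5%, the chance of seeing none in 30 is 0.95^30 = 0.215.

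**3. What the group test could detect.** Two-sided Fisher test, 30 vs 10, with 0/10 events in controls:
- 9/30 operated: the probability that all 9 events fall in the operated group is C(30,9)/C(40,9) = 0.0523. Adding the tables in the other direction that are no more probable (five or more events in controls, 0.0286) gives p = 0.081.
- 10/30 operated: C(30,10)/C(40,10) = 0.0354, plus 0.0074 for six or more events in controls, gives p = 0.043.

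So 10 of 30 (33%) is the smallest significant count. With 1/10 events in controls, the smallest is 15/30 (p = 0.032).

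The uncorrected Chi-square moves this boundary by one patient. At 9/30 vs 0/10, X² = 40 × (9 × 10)² / (30 × 10 × 9 × 31) = 3.87, p = 0.049. At 8/30, X² = 40 × (8 × 10)² / (30 × 10 × 8 × 32) = 3.33, p = 0.068. The choice between the two tests does not change the conclusion.

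**4. Exact power of Fisher's test** (sum of binomial probabilities over all tables with p < 0.05), under assumed true rates:

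| Operated | Non-operated | Power |
|---|---|---|
| 20% | 0% | 0.061 |
| 30% | 10% | 0.150 |
| 20% | 5% | 0.037 |
| 30% | 5% | 0.252 |

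The first row can be checked directly. With no control events, the test rejects only at 10 or more of 30, and P(X ≥ 10) for a binomial with n = 30 and risk 0.20 is 0.061.

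**The case against.** The best defence is that two loosely worded sentences are being set against a plan that is, in substance, descriptive. The formal safety objective is to report type, frequency and severity. Nothing in the protocol says that a non-significant test means the implant is safe. Safety decisions run through benefit-risk re-evaluation (7.4, 9.7, 10.5), expedited reporting (8.3, 8.4) and an independent clinical monitor (8.3), not through Fisher's test. Interval methods are also commonly left to a SAP, which may exist.

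Much of this stands, and it limits the consequence. It does not rescue the claim. The aim is stated twice, once at the head of the statistics section, and the protocol itself fixes group tests as the inferential safety analysis. A SAP could add an interval, but it could not make the stated aim true.

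Three stronger readings are tempting and should not be drawn:
- **Section 4.3 turns a safety p-value into standard use.** It says: "If the trial shows benefit for the patient the procedure will be performed after the trial as standard procedure by the investigator". The trigger is benefit; neither a safety test nor a zero count is mentioned.
- **The planned 20% loss cuts the safety denominator to 24, with an upper limit of 14.2%.** Section 8.3 places the highest risk at surgery, collection starts at the end of the hospital stay (8.4.2), and data up to the point of loss are used (7.1.1, 7.3). Perioperative events are therefore seen in essentially all 30. The 24-patient figure could apply only to late events.
- **The zero-event limit applies to all AEs.** Section 12.1 lists redness, haematoma, swelling, infection and pain as trial-related AEs, so a zero count is realistic only for SAEs.

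**Conclusion.** The point holds as an overclaim: the protocol attributes to the trial a property that its design and its fixed safety analysis do not have. The size of the gap is an SAE risk of up to 11.6% (two-sided 95%) still compatible with a clean record in 30 implants, and a Fisher test that can miss events in 9 of 30 operated patients when controls have none. The confidence limits and the Fisher cut-offs depend only on the group sizes and the stated significance level. The power values depend on the assumed rates, but power is low at each pair shown.

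This is not an arithmetic error, since the score-based power at 30/10 and 24/8 reproduces. It is also not a fault in how safety is monitored during the trial. It should be corrected because it determines what may be concluded and published from the safety data.

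**What to change.** - **Sections 4.1 and 9:** for safety, replace the aim of proving or confirming with describing.
- **Sections 9.3 and 9.5:** make the main safety result the proportion of operated patients with at least one SAE, and likewise with at least one treatment-related event, each with an exact (Clopper-Pearson) 95% interval. Keep the comparison with the non-operated group as descriptive only. Name one test consistently in 9.1, 9.3 and 9.5 if a p-value is still shown.
- **Same sections:** state that a non-significant comparison is not evidence of safety, and that no SAE in 30 implants would still leave a two-sided 95% upper limit of 11.6%.

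The cost is a few sentences, a few lines of analysis and a less favourable stated claim. Sample size, visits, data collection and treatment do not change.
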